6.3.4.3 Clinical Lesions

Clinical lesions will only be considered measurable when they are superficial (e.g., skin nodules and palpable lymph nodes) and ≥ 10 mm diameter as assessed using calipers (e.g., skin nodules). In the case of skin lesions, documentation by color photography, including a ruler to estimate the size of the lesion, is recommended.

6.3.4.4 Methods of Measurement

Chest X-ray - Lesions on chest x-ray are acceptable as measurable lesions when they are clearly defined and surrounded by aerated lung. However, CT is preferable.

CT and MRI - CT and MRI are the best currently available and reproducible methods to measure target lesions selected for response assessment. For this study helical Multi-detector CT will be performed with cuts of 5 mm in slice thickness for chest, abdomen and pelvis lesions and 2-3 mm thickness for head and neck lesions.

6.3.4.5 Additional Response Evaluation Using Volumetric Analysis

In addition, the utility of volumetric tumor measurement in patients with measurable disease will be prospectively evaluated and compared to 1D and 2D measurements.

6.3.5 Response Criteria for Radiographic Studies

6.3.5.1 Measuring of Soft Tissue Disease

a. Evaluation of Target Lesions

Complete Response (CR)

Disappearance of all target lesions. Any pathological lymph nodes (whether target or non-target) must have reduction in short axis to < 10 mm.

Partial Response (PR)

At least a 30% decrease in the sum of the diameters of target lesions, taking as reference the baseline sum diameters.

Progressive Disease (PD)

At least a 20% increase in the sum of the diameters of target lesions, taking as reference the smallest sum on study (this includes the baseline sum if that is the smallest on study). In addition to the relative increase of 20%, the sum must also demonstrate an absolute increase of at least 5 mm. (Note: the appearance of one or more new lesions is also considered progressions).

Note: For this study, determination of PD will not be made prior to the Day 60 evaluation.

Stable Disease (SD)

Neither sufficient shrinkage to qualify for PR nor sufficient increase to qualify for PD, taking as reference the smallest sum diameters while on study.

b. Evaluation of Non-Target Lesions

Complete Response (CR)

Disappearance of all non-target lesions and normalization of tumor marker level. All lymph nodes must be non-pathological in size (< 10 mm short axis).

Note: Tumor markers alone cannot be used to assess response. If tumor markers are initially above the upper normal limit, they must normalize for a patient to be considered in complete clinical response.

Non-CR/Non-PD (Stable Disease, SD)

Persistence of one or more non-target lesion(s) and/or maintenance of tumor marker level above the normal limits.

Progressive Disease (PD)

Appearance of one or more new lesions and/or *unequivocal progression* of existing nontarget lesions. *Unequivocal progression* should not normally trump target lesion status. It must be representative of overall disease status change, not a single lesion increase.

Although a clear progression of "non-target" lesions only is exceptional, the opinion of the treating physician should prevail in such circumstances, and the progression status should be confirmed at a later time by the review panel (or Principal Investigator).

c. Evaluation of Best Overall Response

The best overall response is the best response recorded from the start of the treatment until disease progression/recurrence (taking as reference for progressive disease the smallest measurements recorded since the treatment started). The patient's best response assignment will depend on the achievement of both measurement and confirmation criteria.

Target Lesions	Non- Target Lesions	New Lesions	Overall Response	Best Overall Response when Confirmation is Required*
CR	CR	No	CR	\geq 4 wks. Confirmation**
CR	Non-CR Non-PD	No	PR	\geq 4 wks. Confirmation**
CR	Not evaluated	No	PR	
PR	Non- CR Non-PD Not evaluated	No	PR	
SD	Non- CR Non-PD Not evaluated	No	SD	Documented at least once \geq 4 wks. from baseline**
PD	Any	Yes or No	PD	
Any	PD***	Yes or No	PD	No prior SD, PR or CR
Any	Any	Yes	PD	

For Patients with Measurable Disease (i.e., Target Disease)

* See RECIST 1.1 manuscript for further details on what is evidence of a new lesion.

** Only for non-randomized trials with response as primary endpoint.

*** In exceptional circumstances, unequivocal progression in non-target lesions may be accepted as disease progression.

- d. Patients with a global deterioration of health status requiring discontinuation of treatment without objective evidence of disease progression at that time should be reported as "*symptomatic deterioration*." Every effort should be made to document the objective progression even after discontinuation of treatment.
- e. In some circumstances, it may be difficult to distinguish residual disease from normal tissue. When the evaluation of complete response depends on this determination, it is recommended that the residual lesions be investigated (fine needle aspirate/biopsy) before confirming the complete response status.

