3.1.1 Study Schema

Treatment evaluation including staging studies and biopsy will be performed on Days 64 and 65 +/- 7 days. DAC-THU will be given on two consecutive days as indicated, with Tuesday/Wednesday optimal but not absolute. Pembrolizumab may be administered on Wednesday, Thursday, or Friday for administrative convenience.

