6.3.2 Definitions

Evaluable for toxicity: All patients will be evaluable for toxicity from the time of their first treatment with DAC/THU/pembrolizumab. Dose limiting toxicities will be assessed during the first 3 weeks of DAC-THU/pembrolizumab therapy.

Evaluable for objective response: Patients who have measurable disease present at baseline, have received at least 9 weeks of DAC-THU/pembrolizumab therapy (one full course), and have had their disease re-evaluated will be considered evaluable for response provided: (1) the patient demonstrates progressive disease or death while on protocol therapy; (2) the tumor is not removed surgically prior to the time complete response or partial response is confirmed; or (3) the patient demonstrates a complete or partial response as confirmed according to protocol criteria. These patients will have their response classified according to the definitions stated below. [Note: Patients who electively terminate therapy before completing 9 weeks of DAC-THU/pembrolizumab therapy and do not expire within 14 days from start of treatment will be replaced. Patients who experience disease progression after 3 weeks of drug therapy but before

completing the minimum of 9 weeks of drug therapy will be taken off-treatment and will only be evaluable for toxicity (not evaluable for response)].

Evaluable Non-Target Disease Response: Patients who have lesions present at baseline that are evaluable but do not meet the definitions of measurable disease, have received at least 8 weeks of DAC-THU/pembrolizumab therapy, and have had their disease re-evaluated will be considered evaluable for non-target disease. The response assessment is based on the presence, absence, or unequivocal progression of the lesions.

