Since published data have demonstrated a response rate of 45% for first-line pembrolizumab alone in NSCLC patients with PD-L1 expression of 50% or greater (95), (98), this trial will try to demonstrate if a response rate in excess of 45% may be realized in NSCLC patients with \geq 50% PD-L1 expression by the addition of DAC/THU. Briefly, NSCLC patients with high intratumoral (50% or greater) PD-L1 expression will be evaluated for response as part of a Simon optimal twostage Phase II trial design (116) in order to rule out an unacceptably low PR+CR rate of 35% (p0=0.35) in favor of an improved response rate of 60% (p1=0.60). With alpha=0.10 (probability of accepting a poor treatment=0.10) and beta=0.20 (probability of rejecting a good treatment=0.20), the first stage will determine the response rate in 10 evaluable patients, including those NSCLC patients among the 10 who are treated at the MTD from the Phase I cohort who have high intra-tumoral PD-L1 expression. If 0 to 4 of the 10 patients have a clinical response, then no further patients will be accrued. If 5 or more of these 10 patients have a response, then accrual would continue until a total of 23 evaluable patients have been treated at the MTD. As it may take up to several months to determine if a patient has experienced a response, a temporary pause in the accrual may be necessary to ensure that enrollment to the second stage is warranted. If there are 5 to 10 patients with a response out of 23 patients, this would be an uninterestingly low response rate. If there were 11 or more of 23 (47.8%) who experienced a response, this would be sufficiently interesting to warrant further study in later trials. Under the null hypothesis (35% response rate), the probability of early termination is 75.2%.

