NSCLC patients with low (0-49%) intratumoral PD-L1 expression will be evaluated for response using a Simon optimal two-stage Phase II trial design (116) in order to rule out an unacceptably low PR+CR rate of 10% (p0=0.10) in favor of an improved response rate of 30% (p1=0.30). Variable mutational burdens among NSCLC with low PD-L1 expression could affect responses to immune checkpoint inhibitors, potentially making this cohort more heterogeneous than the NSCLC high PD-L1 expresser cohort. For example, NSCLC patients without activating mutations in EGFR, HER2 or ALK with PD-L1 tumor proportion score (TPS) < 1% have an expected response rate of less than 10%, whereas those with activating mutations involving these genes have response rates of 5% or less; patients with PD-L1 TPS of 1-49% have a 17% response rate (25, 103, 104, 113). Therefore, with alpha=0.05 (probability of accepting a poor treatment=0.05) and beta = 0.20 (probability of rejecting a good treatment=0.20), the first stage will determine the response rate in 10 evaluable patients, including those among the 10 who are treated at the MTD from the Phase I cohort who have low intra-tumoral PD-L1 expression, and if 0 to 1 of the 10 have a clinical response, then no further patients will be accrued. If 2 or more of these 10 patients have a response, then accrual would continue until a total of 29 evaluable patients have been treated in this cohort. As it may take up to several months to determine if a patient has experienced a response, a temporary pause in the accrual may be necessary to ensure that enrollment to the second stage is warranted. If there are 2 to 5 patients with a response out of 29 patients, this would be an uninterestingly low response rate. If there were 6 or more of 29 (20.7%) who experienced a response, this would be sufficiently interesting to warrant further study in later trials. Under the null hypothesis (10% response rate), the probability of early termination is 73.6%.

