10.1 METHODS OF ANALYSIS

Response rates will be calculated as the percent of patients whose best response is a CR or PR. Toxicity information recorded will include the type, severity, time of onset, time of resolution, and the probable association with the study regimen. Tables will be constructed to summarize the observed incidence by severity and type of toxicity.

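### Section 6.3.2 drops early treatment failures from the evaluable set, so both NSCLC Simon designs are judged on a response rate biased upward

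*Combined protocol and SAP*

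**What the plan says.** Section 6.3.2 defines who is evaluable for objective response. The patient needs measurable disease at baseline, at least 9 weeks (one full course) of therapy and a disease re-evaluation. A bracketed note then deals with progression that falls between week 3 and the end of the course. Patients whose disease progresses short of "completing the minimum of 9 weeks of drug therapy will be taken off-treatment and will only be evaluable for toxicity (not evaluable for response". The same note says that patients who electively stop before 9 weeks, and do not die within 14 days of starting, are replaced.

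Section 10 runs both NSCLC cohorts on this set. The first stage is 10 evaluable patients in each. In the high PD-L1 cohort "accrual would continue until a total of 23 evaluable patients have been treated at the MTD"; in the low PD-L1 cohort "accrual would continue until a total of 29 evaluable patients have been treated in this cohort". Section 10.1 adds only: "Response rates will be calculated as the percent of patients whose best response is a CR or PR". It names no analysis set.

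Three other places bear on timing:
- Section 3.1.1: "Treatment evaluation including staging studies and biopsy will be performed on Days 64 and 65 +/- 7 days". No staging scan is scheduled between baseline and that visit.
- Section 3.3.1.1 allows treatment to continue on Day 1 of each cycle only if there is no evidence of progressive disease. For cycles 2 and 3 that check falls before Day 60.
- Section 6.3.5.1, under target-lesion progression: "For this study, determination of PD will not be made prior to the Day 60 evaluation".

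**The concern.** A patient who progresses at week 5 has failed treatment. Under 6.3.2 that patient is not a non-responder but leaves the response analysis, and accrual continues until another evaluable patient fills the place. The progression rule removes only failures, so the response rate among evaluable patients exceeds the rate among treated patients.

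These are single-arm cohorts whose decisions rest on counts of 11 of 23 and 6 of 29. If 35% and 10% are read as rates in patients given the treatment, the probability of declaring an uninteresting regimen positive is higher than the plan states.

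The Day 60 note adds a smaller difficulty. It bars a progression call in a window where 6.3.2 and 3.3.1.1 both act on progression.

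**Working it through.** **Inputs (Section 10).** High PD-L1: p0 = 0.35, p1 = 0.60, stop if 4 or fewer of 10 respond, positive if 11 or more of 23, alpha 0.10. Low PD-L1: p0 = 0.10, p1 = 0.30, stop if 1 or fewer of 10, positive if 6 or more of 29, alpha 0.05. Power is 0.80 in both.

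**Step 1: reproduce the plan.** With stage 1 limit r1 of n1 and final limit r of n, at response probability q:

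PET = P(Bin(n1, q) ≤ r1)

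P(positive) = Σ over k from r1+1 to n1 of P(Bin(n1, q) = k) × P(Bin(n − n1, q) ≥ r + 1 − k)

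- High: PET 0.7515 (plan 75.2%), alpha 0.0977, power 0.8043.
- Low: PET 0.7361 (plan 73.6%), alpha 0.0471, power 0.8051.

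The Simon arithmetic is right. Both designs sit close to their alpha limits, so there is little slack.

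**Step 2: effect of the exclusion.** Let x be the share of treated patients who are excluded. In the limiting case where none of them could have responded, a true rate p0 among treated patients becomes q = p0/(1 − x) among evaluable patients. The decision rules are then applied at q.

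| x (assumed) | High: q | High: alpha | Low: q | Low: alpha |
|---|---|---|---|---|
| 0% | 0.350 | 0.098 | 0.100 | 0.047 |
| 5% | 0.368 | 0.132 | 0.105 | 0.058 |
| 10% | 0.389 | 0.177 | 0.111 | 0.071 |
| 15% | 0.412 | 0.236 | 0.118 | 0.088 |

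At x = 10%, a positive result of 11/23 corresponds to 11 × 0.90/23 = 43.0% of treated patients instead of 47.8%. In the low cohort, 6/29 corresponds to 6 × 0.90/29 = 18.6% instead of 20.7%.

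**Step 3: what x might be.** The documents do not say. For orientation only, assume exponential PFS with pembrolizumab-alone medians from Section 1.2.10 and a 30.44-day month. Progression between days 21 and 63 is then x = 0.5^(21/(30.44m)) − 0.5^(63/(30.44m)) for a median of m months.

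- High, m = 10.3 and 6.1: x = 8.5% and 13.4%, alpha 0.162 and 0.216.
- Low, m = 6.0 and 3.0 (medians across all PD-L1 levels): x = 13.6% and 23.3%, alpha 0.083 and 0.127.

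With no scan scheduled in that window, most of this progression would go unseen. If a quarter of it were recognised, alpha would be 0.111 and 0.119 (high), and 0.054 and 0.060 (low).

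**Step 4: accrual.** Filling 23 + 29 = 52 evaluable NSCLC places takes 52x/(1 − x) extra patients: 2.7, 5.8 and 9.2 at x = 5%, 10% and 15%. The ceiling leaves 85 − 78 = 7 places for all inevaluable patients.

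**The case against.** Four arguments deserve weight.

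**The size is unknown.** This stands. The PFS figures are not a bound: they assume a constant hazard, come from pembrolizumab alone, and count deaths as well as progression. Treating every excluded patient as a certain non-responder is also a limiting case, since growth on an off-schedule scan could later reverse.

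**The null rates might refer to evaluable patients.** Section 10 applies its rules to that set and does not call p0 an all-treated rate. That is why the claim is confined to treated patients. But a benchmark that omits early failures says little about how the regimen performs in those who receive it.

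**6.3.2 may mean only clinical decline.** It does not say so. Section 6.3.5.1 gives decline its own label, symptomatic deterioration: "Patients with a global deterioration of health status requiring discontinuation of treatment without objective evidence of disease progression". Even on that reading, treatment failures leave the denominator.

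**The Day 60 note might govern instead.** A reader might infer that the plan leaves open which of two rules applies, that the choice would be made after progression is seen, and that the effect vanishes if the note prevails. The documents do not support this. The note sits under target-lesion progression, times that category, and says nothing on evaluability; 6.3.2 alone defines the evaluable set. Nor would the note bring the effect to zero, because a patient who stops before 9 weeks still fails the exposure condition and 3.3.1.1 still acts on progression at each cycle.

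**Conclusion.** The point holds. As written, 6.3.2 removes patients who progress after week 3 and before completing 9 weeks. Its exposure condition also removes those who stop earlier for progression or deterioration, and those who die before 9 weeks unless its death clause is read as protecting them. Section 10 then accrues until the evaluable counts are met, so these patients are in effect replaced and the response rate is biased upward.

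The size depends on x, which is likely modest because no scan is scheduled before the first evaluation. The tabulated alphas rest on an assumed x and on no excluded patient being able to respond. A reader might take the larger values as expected error rates; the documents give no basis for that. The direction of the progression-rule bias does not depend on x.

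The Day 60 note is a secondary inconsistency. It would also be too strong to say that progression at the first evaluation is always a final non-response: Section 6.3.3.4 asks for a confirmatory scan unless clinically not indicated, and resets the baseline if progression is not confirmed.

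**What to change.** 1. In 6.3.2, replace the sentence on progression after 3 weeks with: *A treated patient with measurable disease who stops protocol therapy for disease progression, symptomatic deterioration or death before the first treatment evaluation is evaluable regardless of the 9-week exposure requirement, counts as a non-responder, and is not replaced.* Keep replacement only for elective withdrawal without progression.
2. In 10.1, name this set as the denominator for the Simon decision rules.
3. Optionally, in 6.3.5.1, refer to the first treatment evaluation (Section 3.1.1) in place of Day 60, and state that the note does not affect evaluability. Leave the confirmation and re-baselining rule of 6.3.3.4 in force for patients who continue treatment.

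This wording does not cover early stops for toxicity, which also fail the 9-week condition; the amendment should say how they count.

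The cost is a wording amendment, with no added scans and fewer replacement patients. The observed response rate will be slightly lower: at x = 5% and a true rate of 35%, it is 35.0% instead of 0.35/0.95 = 36.8%.

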6.4 TOXICITY CRITERIA

The following adverse event management guidelines are intended to ensure the safety of each patient while on the study. The descriptions and grading scales found in the revised NCI Common Terminology Criteria for Adverse Events (CTCAE) version 5.0 will be utilized for AE reporting. All appropriate treatment areas have access to a copy of the CTCAE version 5.0. A copy of the CTCAE version 5.0 can be downloaded from the CTEP web site (http://ctep.cancer.gov).

7 NIH REPORTING REQUIREMENTS/DATA AND SAFETY MONITORING PLAN

7.1 **DEFINITIONS**

Please refer to definitions provided in Policy 801: Reporting Research Events found here.

7.2 OHSRP OFFICE OF COMPLIANCE AND TRAINING/IRB REPORTING

7.2.1 Expedited Reporting

Please refer to the reporting requirements in Policy 801: Reporting Research Events and Policy 802 Non-Compliance Human Subjects Research found here. Note: Only IND Safety Reports that meet the definition of an unanticipated problem will need to be reported per these policies.

7.2.2 IRB Requirements for PI Reporting Continuing Review

Please refer to the reporting requirements in Policy 801: Reporting Research Events found here.

7.3 NCI CLINICAL DIRECTOR REPORTING

Problems expeditiously reported to the OHSRP in iRIS will also be reported to the NCI Clinical Director. A separate submission is not necessary as reports in iRIS will be available to the Clinical Director.

In addition to those reports, all deaths that occur within 30 days after receiving a research intervention should be reported via email to the Clinical Director unless they are due to progressive disease.

To report these deaths, please send an email describing the circumstances of the death to the Clinical Director/designee at [contact] within one business day of learning of the death.

7.4 NIH REQUIRED DATA AND SAFETY MONITORING PLAN

7.4.1 Principal Investigator/Research Team

The clinical research team will meet weekly when patients are being actively treated on the trial to discuss each patient in detail. Decisions about dose level enrollment and dose escalation if applicable will be made based on the toxicity data from prior patients.

All data will be collected in a timely manner and reviewed by the principal investigator or a clinical associate investigator in a timely manner. Events meeting requirements for expedited reporting as described in Section 7.2.1 will be submitted within the appropriate timelines.

The principal investigator will review adverse event and response data on each patient to ensure safety and data accuracy. The principal investigator will personally conduct or supervise the investigation and provide appropriate delegation of responsibilities to other members of the research staff.

8 SPONSOR SAFETY REPORTING

8.1 **DEFINITIONS**

8.1.1 Adverse Event

Any untoward medical occurrence in a patient or clinical investigation subject administered a pharmaceutical product and which does not necessarily have a causal relationship with this treatment. An adverse event (AE) can therefore be any unfavorable and unintended sign (including an abnormal laboratory finding), symptom, or disease temporally associated with the use of a medicinal (investigational) product, whether or not related to the medicinal (investigational) product (ICH E6 (R2)).

8.1.2 Serious Adverse Event (SAE)

An adverse event or suspected adverse reaction is considered serious if in the view of the investigator or the sponsor, it results in any of the following:

- Death.
- A life-threatening adverse event (see Section **8.1.3**).
- Inpatient hospitalization or prolongation of existing hospitalization.
 - A hospitalization/admission that is pre-planned (i.e., elective or scheduled surgery arranged prior to the start of the study), a planned hospitalization for pre-existing condition, or a procedure required by the protocol, without a serious deterioration in health, is not considered a serious adverse event.
 - A hospitalization/admission that is solely driven by non-medical reasons (e.g., hospitalization for patient or subject convenience) is not considered a serious adverse event.
 - Emergency room visits or stays in observation units that do not result in admission to the hospital would not be considered a serious adverse event. The reason for seeking medical care should be evaluated for meeting one of the other serious criteria.

- Persistent or significant incapacity or substantial disruption of the ability to conduct normal life functions.
- A congenital anomaly/birth defect.
- Important medical events that may not result in death, be life-threatening, or require hospitalization may be considered a serious adverse drug experience when, based upon appropriate medical judgment, they may jeopardize the patient or subject and may require medical or surgical intervention to prevent one of the outcomes listed in this definition.

